### **5.6.6. Visit Windows**

Visit names are presented as collected in the database and no visit windowing will be performed. However, unscheduled visit values will be used for safety analyses of most severe event.

All information collected at an unscheduled visit will be identified as such and presented in the listings.

### **5.6.7. Multiple Assessments**

For laboratory data, where multiple planned measurements are recorded for a given time point, the median of the measurements will be calculated and used in any derivation of summary statistics.

The endpoint data will be summarized for planned visits only. The baseline measurement and all post-baseline data will be listed.

### **5.6.8. Number of Units of Packed RBCs Transfused**

The number of units of pRBCs will be the total count per subject of units of pRBCs or whole blood that are administered to the subject during the study as recorded in the eCRF. Transfusions of 1 unit of whole blood will count as 1 unit of pRBCs.

## **5.7. Handling of Missing Data**

Every effort will be made to obtain all data. There will be no data imputation for missing data except for missing baseline labs. In this case, the first on-treatment value will be used as the baseline.

### **5.7.1. Missing Start and Stop Dates for Concomitant Medication**

For analysis of medications, a complete date should be established to identify medication as occurring during treatment or not. For the purposes of handling partially reported start and stop dates for medication, the following algorithm will be applied:

- Missing start day, but month and year present:  
If study medication had been taken in the same month and year as the occurrence of the medication, then the start day of the medication will be assigned to the day of first dose of study medication.  
Otherwise, the start day will be set to the first day of the month.
- Missing start day and month, but year present:  
If study medication had been taken in the same year as the occurrence of the medication, then the start date of the medication will be assigned to the date of first application of study medication.  
Otherwise, the start day and month will be set to 01 January.
- Missing end day, but month and year present:  
The day will be set to the last day of the month.

- Missing end day and month, but year present:  
The end day and month will be set to the end of study date.

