#### **8.4. End of Study Definition**

The end of the study (EOS) will be defined as the date when the last subject completes the last protocol scheduled visit.

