### **3. STUDY DESIGN**

#### **3.1. Summary of Study Design**

This study is designed to provide continued access to BCX9930 for subjects currently receiving treatment with BCX9930 in another BioCryst-sponsored clinical study for PNH (i.e., Studies 201, 202, or 203, hereafter referred to as the “prior study”) who, in the opinion of the investigator, have both benefited from treatment with BCX9930 and would benefit from continued treatment with BCX9930, who wish to continue treatment, and who do not have access to other effective treatment options.

Subjects will be eligible to receive study drug (BCX9930) under this version of the protocol for up to 96 weeks for as long as the investigator believes it is in the subject’s best interest to continue treatment, or until the subject has access to another therapy for PNH, whichever comes first. Treatment with BCX9930 will be discontinued for subjects who are deriving no meaningful clinical benefit, or who experience an unacceptable drug-related AE or are otherwise intolerant of study drug.

An independent BCX9930 program-wide DMC will provide oversight of the safety of subjects receiving BCX9930 in this study.

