### **5.7.2. Missing Start Date, Stop Date, Severity, or Relationship for Adverse Events**

The same conventions to address incomplete dates for prior and concomitant medications will also be used for AEs. Should an event have a missing severity or relationship, it will be classified as having the highest non-fatal severity (grade 4) and/or strongest relationship to study treatment (related).

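### The partial-date rules in SAP 5.7.1 and 5.7.2 can contradict the recorded year, or put an end before its start, because they are not tied to the first-dose year and month (minor)

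*SAP*

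**What the plan says.** SAP 5.7.1 sets the rules for incomplete medication dates.

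- **Year-only start.** The condition is "If study medication had been taken in the same year as the occurrence of the medication". If it is met, "then the start date of the medication will be assigned to the date of first application of study medication". If not, "Otherwise, the start day and month will be set to 01 January".
- **Month-and-year start.** If study drug was taken in that month and year, "then the start day of the medication will be assigned to the day of first dose of study medication". If not, the first of the month is used.
- **Month-and-year end.** The last day of the month is used.
- **Year-only end.** "The end day and month will be set to the end of study date".

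SAP 5.7.2 adds: "The same conventions to address incomplete dates for prior and concomitant medications will also be used for AEs".

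Three other places matter.

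- SAP 3.1 allows long treatment: "Subjects will be eligible to receive study drug (BCX9930) under this version of the protocol for up to 96 weeks".
- SAP 5.6.5 classes a medication as prior if it ended on or before the first dose. It is concomitant if it started on or after the first Study 205 dose, ended after it, or is ongoing.
- The SAP does not define the end of study date. Protocol 8.4 gives a study-level one, "defined as the date when the last subject completes the last protocol scheduled visit".

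**The concern.** An imputed date should fill in what is missing and leave alone what is known. Nothing in SAP 5.7.1 requires the result to stay in the recorded year or month, or to keep the end on or after the start. The start rules ask whether the subject was on drug in the recorded period, then use a first-dose date that may lie in a different period.

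The outputs at stake are these:

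- the prior versus concomitant classification behind Table 14.1.5.1 and Listing 16.2.4.3;
- onset dates and durations in the listings;
- possibly the split of adverse events between the 400 mg BID and dose taper columns (SAP 8.1 to 8.2.2.2).

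**Working it through.** The plan gives no figure to reproduce, so the check applies the rules to dates. The documents give no first-dose dates; those below are assumptions.

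**Inputs.** First dose 15 Oct 2023 (assumed). Full course 96 × 7 = 672 days (SAP 3.1), so the last dose is 15 Oct 2023 + 671 days = 16 Aug 2025. The end-of-study visit is about 3 weeks later (Protocol 10.1): 16 Aug 2025 + 21 days = 6 Sep 2025.

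**1. Year-only starts.** Drug was taken in 2023, 2024 and 2025, so the condition holds in all three years.

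| Recorded | SAP rule gives | Contradiction |
|---|---|---|
| 2022 | 01 Jan 2022 | none |
| 2023 | 15 Oct 2023 | none |
| 2024 | 15 Oct 2023 | 78 days before 2024 begins |
| 2025 | 15 Oct 2023 | 444 days before 2025 begins |

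78 = 16 days left in October + 30 + 31 + 1. 444 = 78 + 366.

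In a listing, an event with start 2024 and known end 10 Mar 2024 would begin on Study Day 1 and last 148 days. From 01 Jan 2024 it would begin on Study Day 79 and last 70 days.

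**2. How much of treatment is exposed.** The contradiction needs a recorded year after the first-dose year in which drug was taken. With first dose spread evenly over a calendar year, the share of treatment days in a later calendar year is about 73% for a 96-week course (range 46% to 99.9% by first-dose date), 46% for 48 weeks and 23% for 24 weeks. These are shares of treatment time, not of records.

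**3. Month-and-year starts.** If only the day is borrowed, a start recorded as March 2024 becomes 15 Mar 2024. With a known end of 10 Mar 2024, the start falls after the end. A first dose on the 31st would give 31 April, which does not exist. If the full first-dose date is meant, the recorded month is overwritten instead.

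**4. Year-only ends.** The wording sets the day and month to a full date, which leaves two readings. Taking the subject's own end of study (6 Sep 2025):

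| Recorded end | Reading A: full date | Reading B: year kept |
|---|---|---|
| 2022 | 6 Sep 2025, 980 days past year-end; concomitant | 6 Sep 2022; prior |
| 2023 | 6 Sep 2025, 615 days past year-end; concomitant | 6 Sep 2023, 39 days before first dose |
| 2024 | 6 Sep 2025, 249 days past year-end; concomitant | 6 Sep 2024; concomitant |

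Reading A makes a drug stopped in 2022, before entry, concomitant. Under Reading B, a drug started in an earlier year with an end recorded only as 2023 becomes prior, although it may have run past first dose. If its start is also recorded only as 2023, the start becomes 15 Oct 2023 and the end 6 Sep 2023. The end precedes the start, and the record meets both definitions in SAP 5.6.5.

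**5. What does not change.** For a later on-drug year, both the first-dose date and 01 January of that year lie between first and last dose. TEAE status, the 30-day post-dose exclusion (SAP 5.6.4) and concomitant status by start date are therefore the same under either date.

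**The case against.** The strongest defence is that the flaw hardly reaches the planned tables, and much of it stands.

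- **TEAE counts.** The endpoint is subject incidence, and no table summarises onset day or duration. Step 5 confirms that the start flaw leaves TEAE totals alone.
- **End rule.** The parallel 01 January wording plainly keeps the recorded year, so Reading B is natural. A reader might infer that old medications are certainly counted as concomitant; the text does not establish that. But Reading B has its own failure, so choosing it does not rescue the rule.
- **Size.** A reader might say that a 2024 start is moved 78 to 443 days too early. That compares the imputed date with an unknown true date. Using 01 January would still be 0 to 365 days early; the flaw itself adds 78.
- **Taper column.** A reader might infer that taper events generally shift to 400 mg BID. A year-only taper event set to 01 January also lands there unless a taper was under way that day. The SAP does not say how events are assigned to columns, and the taper details are blacked out.
- **Reach.** It is not true that treatment always spans two calendar years, since 96 weeks is a maximum. Nor are all later-year starts misdated: if no drug was taken that year, 01 January applies.
- **Records.** Medications are recorded from the baseline visit (Protocol 9.8) and adverse events from enrollment (Protocol 12.4), with visits every 4 to 12 weeks. Year-only on-treatment onsets should be rare, and pre-entry adverse events lie outside the collection period. Medication history does come from the prior study, so partial pre-entry medication dates remain plausible.

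The authors may have meant first dose in the same year. The SAP does not say so.

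**Conclusion.** The rules are wrong as written, and the consequence is minor. On the literal wording, a year-only start in an on-drug year after the first-dose year contradicts its recorded year. The month-only rule can give a start after a known end, an impossible date or an overwritten month. The year-only end rule fails on both readings, and the SAP does not say whether it means the study's or the subject's own end of study.

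What can change is prior versus concomitant status (through the end rule), listed onset and duration, and occasionally the 400 mg BID versus dose taper column. With at most 30 subjects, one reclassified subject is at least 1/30 = 3.3 percentage points in a safety-population table.

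The conclusion rests on the literal wording and on some subjects being treated across a calendar year-end. The dates are illustrative. The number of affected records is not in the documents and is probably small. They do not support a claim that TEAE totals are materially wrong.

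**What to change.** Replace the partial-date rules in SAP 5.7.1, keeping the extension to adverse events in 5.7.2, with wording such as:

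> If the known year (and month, if known) equals that of the first Study 205 dose, impute the start as the first-dose date, unless the recorded end is before first dose. Otherwise use the first day of the known month or 01 January of the known year. Impute a partial end as the last day of the known month or 31 December of the known year, capped at the subject's own end-of-study date. No imputed date may contradict a recorded part or place the end before the start.

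In the example, starts of 2024 and 2025 become 01 Jan 2024 and 01 Jan 2025. Ends of 2022, 2023 and 2024 become 31 December of each year, so the 2022 drug is prior and the other two are concomitant. An end of 2025 becomes 6 Sep 2025.

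The cost is a few SAP sentences and minor programming. Partial dates remain approximate, and a month-only taper event may still fall in the 400 mg BID column. It can even move there: with first dose on the 15th of a month and an assumed taper from 10 to 24 June, a June start is 15 June (taper) under the present rule, if it borrows only the day, and 1 June (400 mg BID) under the new one.

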### **5.7.2. Missing Start Date, Stop Date, Severity, or Relationship for Adverse Events**

The same conventions to address incomplete dates for prior and concomitant medications will also be used for AEs. Should an event have a missing severity or relationship, it will be classified as having the highest non-fatal severity (grade 4) and/or strongest relationship to study treatment (related).

### **5.7.3. Missing Time of First Dose**

In case of missing time for first dose, it will be assumed that baseline measures that were to be taken prior to first dose according to the protocol were in fact taken prior to dosing.

### **5.7.4. Transfusion-impacted Period**

The 14-day period following a transfusion of pRBCs or whole blood is defined as the transfusion-impacted period (i.e., the interval between the transfusion day and the current study day is  $\leq$  13 days and includes the day of transfusion). An exception to this rule is that the transfusion-impacted period for haptoglobin is the 3-day period following a transfusion (i.e., the interval between the transfusion day and the current study day is  $\leq$  2 days and includes the day of transfusion).

The following parameters are impacted by pRBC or whole blood transfusion:

- Hemoglobin
- Reticulocytes
- PNH RBC (Type II and III red blood cells)
- Ratio of PNH RBC to PNH WBC
- Haptoglobin (transfusion-impacted period is limited to 3 days instead of 14)

## **6. STUDY POPULATION**

### **6.1. Subject Disposition**

The subject disposition table for all subjects will summarize the number and percentage of subjects that received at least one dose of study drug, discontinued treatment, the reasons for discontinuation, and subjects that completed the study. Results will be summarized for the BCX9930 treatment group.

The percentages for subjects dosed, discontinued, and completed will be based on the number of subjects enrolled. Percentages for discontinuation reason will be based on the number of subjects that discontinued.

### **6.2. Demographic and Baseline Characteristics**

The subject demographic and baseline characteristics table for the subjects in the safety population will descriptively summarize results for age at consent, race, ethnicity, and sex. Results will be summarized for the BCX9930 treatment group.

### **6.3. Concomitant Medications**

Medications will be coded using the World Health Organization (WHO) drug dictionary version B3 March 2021, and summarized by Anatomical Therapeutic Class (ATC) 4 term, preferred term (PT), and treatment group.

#### **6.3.1. Summary of Concomitant Medications**

The concomitant medications table for the subjects in the safety population will summarize the number and percentage of subjects taking concomitant medication(s) by ATC 4 term and PT. The results will be presented for the BCX9930 treatment group.

### **6.4. Exposure to Study Treatment**

The exposure to study treatment table for the subjects in the safety population will descriptively summarize the BCX9930 400 mg BID, dose taper and Total with the number and percentage of subjects dosed and descriptive statistics (i.e., mean, standard deviation, etc.) for the number of days of exposure.

The compliance data as reported on the eCRF will be listed.

## 7. EFFICACY

All study efficacy data in the aCSR will be presented in data listings.

Hypothesis testing will not be conducted due to sponsor discontinuation of the program. No subgroup analyses are planned.

### 7.1. Efficacy Analysis of Hemoglobin

Descriptive statistics for the observed values and changes from baseline in hemoglobin in the safety population will be presented for all scheduled visits during the treatment period. Values recorded within 14 days after the subject received a pRBC or whole blood transfusion will be excluded from the summary statistics. Unscheduled visits will be presented in the data listings but not summarized in the table.

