## 7.4. Individual and Study Termination Criteria

#### 7.4.1. Subject Withdrawal from Study Treatment

A subject will be permanently discontinued from BCX9930 for any of the following reasons:

- Invasive meningococcal infection or invasive encapsulated bacterial infection. Discontinuation of BCX9930 may occur after subject stabilization to prevent uncontrolled hemolysis.
- In the investigator's opinion, it is in the best interest of the subject to discontinue from further dosing.
- Subject noncompliance (eg, protocol deviation), as assessed by the sponsor or investigator, to be detrimental to study or subject benefit-risk profile.
- In the opinion of the investigator or sponsor, the subject is no longer receiving meaningful clinical benefit from continued treatment with BCX9930, or the subject qualifies for treatment with an available alternative therapy for PNH.
- Subject pregnancy
- Discontinuation at the request of the sponsor, relevant competent authority, or the governing institutional review board (IRB), research ethics board (REB), or independent ethics committee (IEC), collectively referred to as "ethics committee".

The reason for discontinuation of study treatment will be recorded in the source documents and electronic case report form (eCRF).

Subject who discontinue treatment with BCX9930 will not be allowed to re-enroll in the study or restart treatment with BCX9930 at a later date following a change in circumstances (eg, after a pregnant subject delivers her baby or a subject discontinues alternative therapy for PNH, including after completion of or discontinuation from a clinical study of another investigational agent for PNH).

Subjects who discontinue study drug for any reason will be monitored for hemolysis as described in Section 12.5.3.

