## 10. STUDY CONDUCT

### 10.1. Overview

Subjects who meet all of the inclusion and none of the exclusion criteria can be enrolled into Study 205. Prospective subjects should have completed at least 12 weeks treatment with BCX9930 in the prior study. The last on-treatment visit completed for the prior study will also serve as the baseline visit for Study 205. Therefore, procedures at the last on-treatment visit in the prior study and any specific assessments for Study 205 that may be needed will be conducted at this visit. (Note: With the expected overlap in study procedures, it is anticipated that few, if any, specific procedures for Study 205 will need to be completed. Please contact the sponsor medical monitor [or designee] if this is unclear). If subjects have completed at least 24 weeks of BCX9930 treatment in the prior study, study visits will occur every 8 weeks to Week 48, then every 12 weeks until Week 96. Subjects who have not completed 24 weeks of treatment with BCX9930 prior to entering this study must return to the clinic every 4 weeks until they have completed 24 weeks of cumulative treatment with BCX9930. More frequent monitoring may be required for subjects with any ongoing safety concern, including [CC1]

Additional visits may be required for subjects who experience hemolysis on study or who require unscheduled visits for additional or repeat evaluations. Additional visits will be required in the case of [CC1] for additional detail).

Subjects who discontinue dosing with BCX9930 for any reason (complete study visits or discontinue early), will be asked to complete an EOS or ET visit, as applicable, approximately 3 weeks ( $\pm$  3 days) after last dose of BCX9930.

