### 7.2. Other Efficacy Endpoints

#### 7.2.1. Percent CFB in Lactate Dehydrogenase (LDH)

Descriptive statistics for the observed values, changes from baseline, and percent changes from baseline in LDH in the safety population will be presented for all scheduled visits during the treatment period. Unscheduled visits will be presented in the data listings but not summarized in the table.

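### By-visit hemoglobin and LDH means describe only subjects still on drug, so later visits may overstate maintenance of effect; a last on-treatment row would show the difference.

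*SAP*

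**What the plan says.** SAP 7.1 plans observed values and changes from baseline in hemoglobin, which "will be presented for all scheduled visits during the treatment period". SAP 7.2.1 does the same for LDH and adds percent change: "percent changes from baseline in LDH in the safety population will be presented for all scheduled visits during the treatment period". In both sections off-schedule readings stay out of the table: "Unscheduled visits will be presented in the data listings but not summarized in the table". For hemoglobin only, SAP 7.1 also drops values within 14 days after a red-cell or whole-blood transfusion. SAP 5.7 allows no imputation except for a missing laboratory baseline, and Protocol 13.3.2 runs by-visit summaries only until a subject completes or withdraws.

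Among the reasons for permanent discontinuation, Protocol 7.4.1 lists that, in the opinion of the investigator or sponsor, "the subject is no longer receiving meaningful clinical benefit from continued treatment with BCX9930". The same item adds a different reason, that "the subject qualifies for treatment with an available alternative therapy for PNH". SAP 3.1 repeats the first: "Treatment with BCX9930 will be discontinued for subjects who are deriving no meaningful clinical benefit". Under Protocol 7.4.1 a subject who stops may not restart. Protocol 10.1 says that subjects who stop "will be asked to complete an EOS or ET visit, as applicable, approximately 3 weeks" after the last dose. Table 2 of the protocol puts that visit in its own column, outside the treatment period.

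**The concern.** A subject who stops drops out of every later row of both tables. Protocol 11.4 leaves benefit to the investigator's judgement and names hemoglobin and LDH among the laboratory measures that inform it. The variable being tabulated can therefore help decide who stays in the table. If subjects who do worse leave more often, the mean of those who remain looks better than the mean over everyone treated.

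Two other features can work the same way. Subjects with worsening hemolysis symptoms may be seen off schedule, and scheduled visits are 12 weeks apart after Week 48 (Protocol 10.3), so a loss of response can arise and lead to stopping between two rows. The transfusion exclusion is sensible for the single value, but it removes from the row a subject who has just needed blood.

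These are the only efficacy tables in SAP 9.1.1. A reader of the abbreviated report who looks for evidence on durability will look there.

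**Working it through.** The documents give no power, effect size, variability or discontinuation rate, so there is no planned figure to reproduce. Only N, up to 30 (SAP 3.3), and the ten visits at Weeks 8 to 96 (Protocol Table 2) come from the documents. Everything else below is assumed.

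**Step 1: arithmetic.** Let d of N subjects stop for lost benefit, with a last on-treatment hemoglobin D g/dL below the mean m of the rest. Assume that all d have left by the late visit, and that anyone who leaves for other reasons resembles those who stay.

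- Mean in the late-visit row: m
- Mean of the last on-treatment value over all subjects: m − D × d/N
- Overstatement: D × d/N

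| d of 30 | D (g/dL) | D × d/30 (g/dL) |
|---|---|---|
| 0 | any | 0 |
| 3 | 1 | 0.1 |
| 3 | 2 | 0.2 |
| 6 | 2 | 0.4 |
| 6 | 3 | 0.6 |
| 9 | 3 | 0.9 |

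**Step 2: simulation with gradual stopping.** Step 1 removes every failing subject before the late row. In practice a fall can be recorded at a scheduled visit before it leads to stopping. Assumptions: N = 30, ten visits, 4,000 runs, reading SD 0.8 g/dL, a fraction f of subjects with a 2 g/dL fall starting uniformly over 96 weeks, and stopping with probability p after any reading more than 1.5 g/dL below baseline.

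| f | p | Week 96 change, all subjects | Week 96 change, still on drug | Gap | Mean n at Week 96 |
|---|---|---|---|---|---|
| 10% | 0.5 | −0.20 | −0.07 | 0.13 | 24.4 |
| 10% | 1 | −0.20 | −0.04 | 0.16 | 20.9 |
| 20% | 0.5 | −0.40 | −0.16 | 0.24 | 22.7 |
| 20% | 1 | −0.40 | −0.08 | 0.32 | 19.0 |
| 40% | 0.5 | −0.80 | −0.36 | 0.44 | 19.1 |
| 40% | 1 | −0.80 | −0.21 | 0.59 | 15.2 |

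With p = 0 the two means agree at every f. Some simulated subjects stop on a chance low reading: at f = 10% and p = 1, 30 − 20.9 = 9.1 have stopped, although only 3 are expected to lose benefit.

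**Step 3: a decline shared by all.** If every subject falls by 1 g/dL by Week 96, the on-drug mean is −1.00 for p = 0, 0.5 and 1, although mean n drops from 30 to 18.4 and 10.9. Here stopping depends only on reading error, so it selects nobody. Bias needs lasting differences between those who stop and those who stay.

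**LDH.** The same reasoning applies with the sign reversed: later means could look too low. The documents give nothing from which to scale it.

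**The case against.** A reader might infer that the tables show a maintained effect whatever happens, or that late visits hold responders only. The documents do not support either reading.

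- Protocol 7.4.1 sets no hemoglobin or LDH level at which a subject must leave, and none appears elsewhere in the visible text. Stopping for lost benefit rests on opinion, so a subject with a falling value or partial benefit can stay.
- A fall seen at a scheduled visit counts in that row. In Step 2 the on-drug mean still declined, and in Step 3 it showed the whole decline.
- Subjects also leave for alternative therapy, adverse events, pregnancy or non-compliance. Those leavers may be doing well.

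Much is also already planned. Protocol 13.3.2 makes n a default statistic, SAP 6.1 tabulates reasons for discontinuation, and the listings give disposition, transfusions, and hemoglobin and LDH results by subject. With at most 30 subjects, a careful reader could trace each leaver. Efficacy is neither an objective nor an endpoint, nothing is tested, and neither document claims durability.

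These points limit the size and importance of the problem. They do not remove it: the overall reasons in the disposition table are not linked to visit rows, and no table shows where the leavers ended.

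**Conclusion.** The by-visit means are observed-case summaries conditional on remaining on drug, and they may overstate maintenance of effect. The direction follows from the plan if some subjects stop because their values have worsened. The size cannot be known from the documents: it is zero if nobody stops for lost benefit, and about 0.1 to 0.9 g/dL under the assumed numbers of leavers and hemoglobin gaps. The 0.9 figure needs 30% of the cohort to stop with a 3 g/dL deficit and none of them to remain in the late row. With gradual stopping the simulated gap was 0.13 to 0.59 g/dL, and the top of that range needed 40% to lose benefit. This is a cheap improvement of minor priority, not a flaw in the study's safety objective.

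**What to change.** Amend SAP 7.1, 7.2.1 and Tables 14.2.1.1 and 14.2.2.3 before database lock:

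1. Add a last on-treatment value row for all safety-population subjects with a post-baseline value: observed value and change from baseline, plus percent change for LDH. Include unscheduled values.
2. Define the row. Use the last value before any dose taper, and say whether local-laboratory values count. This needs stating because SAP 5.5.1, under the baseline definition, limits hemoglobin to central-laboratory values, while Protocol 11.5.4 lets sites use local laboratories. For hemoglobin, show the row with and without the 14-day transfusion exclusion; otherwise it may lose the same subjects again.
3. Note the row as an exception to SAP 5.6.7, which summarizes planned visits only.
4. Beside n at each visit, show cumulative discontinuations by reason.
5. Footnote that by-visit means describe subjects still on treatment and should not be read as durability.

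All of this uses data already collected. It needs no new visits and no imputation of values after stopping. The cost is a few lines of programming and the definitions in item 2. The one statistical drawback is that the last value falls at different times in different subjects, so the row complements the by-visit rows and does not replace them.
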